Does VeraFlo with Prontosan® decrease time to wound and fracture healing in patients with infected lower extremity fractures with indwelling hardware?

Principal Investigator: [name]

Sponsor:

University of Missouri
Orthopaedic Surgery
[name]
[contact]
[name]

Funding Company: KCI USA, Inc.

Hypothesis: Prontosan instillations will decrease time to wound and fracture healing and decreases bacterial load.

Null Hypothesis: Prontosan instillations do not decrease time to wound and fracture healing and decrease bacterial load.

Background: Surgical site infections (SSIs) are a devastating and relatively common surgical complication, occurring in 2% to 5% of patients undergoing surgery in the United States. SSIs can significantly increase patient morbidity, hospital stay duration, healthcare costs, and patient mortality (Anderson 2011). Negative Pressure Wound Therapy (NPWT) with Vacuum-Assisted Closure (VAC) is an established adjunctive treatment option for open wounds that offers the ability to promote healing. However, there is limited evidence for its utility with active infections. Wounds that are acutely infected or that contain an adherent biofilm present a challenging problem (Kim et al 2015).

Wound VAC therapy involves cleaning the wound, applying a custom-fit foam to cover the wound, placing a transparent drape over the wound and adjacent skin, and attaching tubing to connect the foam to a VAC suction canister. NPWT is achieved with a pulling force supplied by the VAC suction canister. Typically, suction will remain at a constant pressure until the dressing is removed. Continuous VAC therapy was recently reported to be more effective than standard moist wound care in surgical site infection after ankle surgery (Zhou et al. 2015). VAC therapy with instillations is a novel treatment option that provides the combination of negative pressure with intermittent instillation of a solution. Polihexanide (Prontosan®) is a modern antiseptic that combines a broad antimicrobial spectrum with low toxicity, high tissue compatibility, no reported adsorption and good applicability as solution, gel, ointment, foam and in wound

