Bacterial load (organism quantities are listed as scant, moderate, or heavy), identification of organism, and susceptibility will be analyzed and reported by the University of Missouri Hospital Laboratory, via semiquantitative wound culture(s) done at each debridement procedure. A maximum of 3 wound cultures will be used for the purposes of research, and the sponsor will cover the cost of up to 3 wound cultures. The culture will be done in the OR, after negative pressure dressing removal, prior to surgical prepping.

The subject will sign consent, be enrolled, and then be randomized at the pre-operative/screening visit. During the initial surgical debridement procedure, information about the wound characteristics, the wound culture results, and information about the dressing that is placed in the OR will be collected for research purposes.

Wound healing will be evaluated at weekly intervals until the sutures are removed and the wound is deemed healed. To assess wound healing, weekly photos of the wound/incision will be done either in clinic, or will be obtained from the subject after they take the photo at home. When applicable, weekly phone visits will be completed to obtain a photo of the incision, (starting after discharge from the hospital), until the subject returns for their SOC clinic visit for suture removal (around 3 weeks post-op). The wound/incision will be assessed with a VAS Incision Healing Assessment Form.

Clinical follow-up visits will be standard after wound healing with clinical radiographs to document fracture healing--6 weeks after initial surgery (+/- 1 week), 3 months (+/-1 week), 6 months (+/-2 weeks), and 12 months (+/-2 weeks) or until fracture healing with minimum of 6 months f/u. Any further debridement or procedures done for fracture healing, including bone stimulator use, will be documented. A clinical photo(s) will be taken at all visits following the initial surgical debridement to document wound healing.

Primary Endpoints:

1. Time to wound and fracture healing (indicating successful resolution of infection)
2. Bacterial load (organism quantities are listed as scant, moderate, or heavy)

Secondary Endpoints:

Number of surgeries:

1. # of operative debridements until wound healed
2. # of surgeries for fracture healing (nonunion and bone grafting)
3. VAS (Incision Healing Assessment Form) scores, based on standardized digital image

Inclusion/Exclusion Criteria

Inclusion:

- Patients 18 years and older

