 - resulted in a life-threatening illness or injury,
 - resulted in permanent impairment of a body structure or body function,
 - required inpatient hospitalization or prolongation of existing hospitalization, or
 - resulted in medical or surgical intervention to prevent permanent impairment to a body structure or a body function.
 - Led to fetal distress, fetal death or a congenital anomaly or birth defect.

The following clarifications are provided for the serious adverse events:

- Life-threatening means that the subject was, in the view of the Investigator, at immediate risk of death from the event as it occurred. The definition does not include an event that, had it occurred in a more severe form, might have caused death.
- Hospitalization for elective treatment of a pre-existing condition that did not worsen during the study is not considered a serious adverse event.
- "Inpatient" hospitalization means the subject has been formally admitted to a hospital for medical reasons. This may or may not be overnight. It does not include presentation at a casualty or emergency room.
- Important medical events that may not result in death, or be life-threatening, however based upon appropriate medical judgment, may jeopardize the subject and may require medical or surgical intervention to prevent one of the outcomes listed in this definition.
- Is significant for any other reason.

Anticipated Adverse Events:

Anticipated adverse events are those events that are reasonably expected to occur as a result of the subject's disease state or treatment. For this study, anticipated

adverse events associated with the procedure or post-procedure include, but are not limited to, the following;

- Infections, both deep and superficial
- Allergies or other reaction to device materials
- Temporary or permanent nerve damage as a result of pressure or hematoma.
- Cardiovascular complications including venous thrombosis, pulmonary embolism, and cardiac arrest.
- Wound hematoma and delayed wound healing.

Device-related adverse events are those events that can be directly attributed to the study device and are adjudicated as such by the Investigator. These events may include, but are not limited to:

- Infections, both deep and superficial
- Allergies or other reaction to device materials
- Loosening of the implant as a result of changed condition in load transfer, respectively fatigue wear or tissue reaction to implant or as result of inadequate anchoring technique.

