- Dislocation, subluxation or inadequate scope of movement as a result of failure to achieve optimum positioning of the implant.
- Bone fractures as a result of one-sided overload or weakened bone structure.
- Temporary or permanent nerve damage as a result of pressure or hematoma.
- Wound hematoma and delayed wound healing.

Unanticipated Adverse Events:

An Unexpected Adverse Experience (UAE) is defined as any adverse reaction, the nature and severity of which is not consistent with the applicable product information. These events will be documented as described below.

An Unexpected Adverse Device Effect (UADE) is defined as any adverse effect on the study subject's health or safety, or any life-threatening problem or death caused by or associated with the device. Also, the effect must not have been previously identified in the Investigational Plan or Instructions for Use in its nature, frequency or severity. UADEs may also include other serious problems associated with the device that affect the rights or welfare of study subjects.

Adverse Event Documentation:

The Principal Investigator or designee will report adverse events for the study analysis. Adverse events will be evaluated and differentiated by:

- Severity of the event, defined below.

- Mild: Awareness of signs and symptoms, but easily tolerated; are of minor irritant type, causing no loss of time from normal activities; symptoms would not require medication or a medical evaluation; signs and symptoms are transient.
- Moderate: Discomfort severe enough to cause interference with usual activities; requiring treatment, but not extended hospitalization or intensive care for the subject.
- Severe: Incapacitating with inability to do work or usual activities; signs and symptoms may be systemic in nature or require medical evaluation and/or treatment; requiring additional hospitalization or intensive care (prolonged hospitalization).
 - Serious Code, as defined in Section “Serious Adverse Events”
 - Relatedness to the device or procedure, defined as:
 - Unrelated: AE is due to the underlying disease state or concomitant medication or therapy not related to the study-specific devices or procedures.
 - Probably not Related: AE had minimum or no temporal relationship to the study-specific devices or procedures and/or more likely alternative etiology exists.

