 - Possibly Related: AE had a strong temporal relationship to the study-specific devices or procedures and alternative etiology is equally or less likely compared to the potential relationship to the study-specific devices or procedures.
 - Probably Related: AE had a strong temporal relationship to the study-specific devices or procedures and another etiology is unlikely.
 - Unknown: Relationship of the AE to the study-specific devices or procedures and alternative etiology is unknown.

Any severe adverse event or device related unanticipated advent must be reported to the study Sponsor by telephone or fax within 24 hours of the event. Additionally, the full details of the event will be documented in the study data base and with a follow up fax if the details of the event cannot be enter into the database promptly. Arthrex Inc. will submit the applicable reports required by each reviewing regulatory authority when appropriate.

Unanticipated Adverse Device Effect (UADEs):

A UADE is any SAE on health or safety or any life-threatening problem or death caused by, or associated with, a device, if that effect, problem, or death was not previously identified in nature, severity, or degree of incidence in the investigational plan or application (including a supplementary plan or application), or any other unanticipated serious problem associated with a device that relates to the rights, safety, or welfare of subjects (21 CFR 812.3).

Expectedness

All Serious Adverse Events will be assessed for expectedness based on the following definitions:

- Expected, Anticipated: the effect, problem, or death had been previously identified in nature, severity, or degree of incidence in the study or product documentation.
- Unexpected, Unanticipated: if that effect, problem, or death was not previously identified in nature, severity, or degree of incidence in the study or product documentation

UADE Reporting to KCI, USA Inc.

UADEs and SAEs must be reported by the Investigator to KCI and the reviewing Institutional Review Board (IRB) per their reporting requirements.

Risks Associated With NPWT Therapy/Dressing

Risks	Disorders/Conditions

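### Two safety-reporting rules are wrong as written: regulatory filing is assigned to a company with no other role, and the 24-hour sponsor notice depends on severity, not seriousness

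*Protocol*

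**What the plan says.** The title block of the protocol lists the University of Missouri, Orthopaedic Surgery, as sponsor and then "Funding Company: KCI USA, Inc". No other company is introduced as a party to the trial.

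Two operative rules close the section Adverse Event Documentation:

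- **Notice to the sponsor:** "Any severe adverse event or device related unanticipated advent must be reported to the study Sponsor by telephone or fax within 24 hours".
- **Regulatory filing:** "Arthrex Inc. will submit the applicable reports required by each reviewing regulatory authority when appropriate".

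Earlier in that section, events are graded mild, moderate or severe. Seriousness is a separate item, "Serious Code, as defined in Section", which points back to Serious Adverse Events. That section defines seriousness by outcome. Among its criteria are that the event "resulted in permanent impairment of a body structure or body function" or "resulted in medical or surgical intervention to prevent permanent impairment to a body structure or a body function". The moderate grade covers events "requiring treatment, but not extended hospitalization or intensive care for the subject".

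One further route exists. UADE Reporting to KCI, USA Inc. requires the investigator to send serious adverse events and unanticipated adverse device effects (UADEs) to KCI and the reviewing IRB, following the requirements of those bodies. It gives no number of hours and does not mention the sponsor.

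**The concern.** These are instructions that site staff are meant to follow when a patient is harmed. Followed literally, the first sends the regulatory filing duty outside the trial: neither the named sponsor nor the funder holds it. The second starts the 24-hour clock on how intense an event is, while the protocol's own outcome-based definition of a serious event sets no such clock. Some serious events would then reach the sponsor with no stated deadline. What is at stake is prompt and correctly addressed safety notice. The comparison of the two groups is not involved.

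A statistical analysis plan, if one exists, would not cure this, because the assignment of reporting duties belongs in the protocol.

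**Working it through.** The plan gives no figure to reproduce and no arithmetic applies. The check sets the rules side by side.

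**1. Who files with the regulator**

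| Party | Role given in the protocol | Filing duty given? |
|---|---|---|
| University of Missouri | Sponsor (title block) | No |
| KCI USA, Inc. | Funder (title block); receives reports of serious events and UADEs | No |
| Arthrex Inc. | None | Yes (Adverse Event Documentation) |

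The sentence that assigns the duty is complete, and the sponsor and funder lines in the title block are intact. Lost or removed text therefore does not explain the mismatch.

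**2. What starts the 24-hour clock**

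There are two triggers: (a) an adverse event graded severe; (b) an event that is both device-related and unanticipated. This is the reading kindest to the plan. If *severe* also governed (b), the rule would cover less.

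For a serious event to miss both triggers, it must be graded below severe, and it must be either anticipated or not device-related. Can the protocol's definitions allow that?

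- Serious Adverse Events makes permanent impairment, and intervention to prevent it, serious in themselves. Neither criterion requires a hospital stay or a particular grade.
- The moderate grade allows treatment and excludes only extended hospitalization or intensive care.
- Nerve damage, temporary or permanent, is on the list under Anticipated Adverse Events.

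| Event | Serious? | Trigger (a) | Trigger (b) | 24-hour notice? |
|---|---|---|---|---|
| Permanent nerve damage, treated, no extended stay, graded moderate, judged anticipated | Yes | No | No | No |
| Intervention to prevent permanent impairment, graded moderate, not device-related | Yes | No | No | No |
| Serious event graded severe | Yes | Yes | Either | Yes |
| Device-related unanticipated event, any grade | Either | Either | Yes | Yes |
| Event graded severe that meets no serious criterion | No | Yes | Either | Yes |

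The first two rows show the gap. The last shows the reverse mismatch. The set of events under the 24-hour rule and the set of serious events overlap but are not the same.

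A short inpatient admission is a less certain example. It is serious by definition, but the severe grade also refers to additional hospitalization, so the grade it would receive is arguable.

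**3. Who receives the notice**

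The title block makes the University the sponsor. Study Design says "the sponsor will cover the cost of up to 3 wound cultures", which would also fit the funder. The party meant by the study sponsor in the 24-hour rule therefore needs confirming.

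**The case against.** The strongest reply is that little is lost in practice.

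- **Many serious events will be graded severe.** That grade covers incapacity, additional hospitalization and intensive care, and its mention of evaluation or treatment overlaps with moderate. This stands, and it makes the gap partial. It does not close it, because the grade opens with incapacity and a serious outcome need not incapacitate.
- **Every serious event still goes to KCI and the IRB.** This stands. A reader might infer that serious events could go unreported altogether, and the documents do not support that. But this route states no hours and does not name the sponsor.
- **The consequence is small whoever the sponsor is.** If KCI is meant, it already receives every serious event and only the timing is open. If the University is meant, its own hospital laboratory and IRB are in use and the delay may be short. This is fair, and it limits the harm. It also shows why the recipient should be named.
- **The nerve-damage example is a chosen case.** It has to be graded moderate and judged anticipated, and the same injury could be graded severe. True: it shows that the gap exists, not how often it occurs.

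Two further readings are tempting and go too far. One is to count how many of the serious criteria escape the rule. No firm count follows from the text: the fetal criterion also needs no hospital stay, and two items listed as clarifications (important medical events, and events significant for another reason) read like criteria. The other is to infer from the stray company name and the implant items in the device-related list that the section was carried over from another protocol. That may be so, but the documents do not say it. These patients have indwelling hardware, the list is expressly not exhaustive, and attribution is left to the investigator's adjudication.

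**Conclusion.** Both rules are wrong as written and should be corrected. The filing duty is held by a company with no stated role; this rests on the text alone. The 24-hour rule uses the intensity grade where the protocol has a separate code for seriousness. It leaves without timed sponsor notice any serious event that is graded below severe and is anticipated or not device-related.

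The second conclusion assumes that grade and seriousness are assigned independently, as the protocol's separate items imply, and that an event on the anticipated list may be judged anticipated.

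The rules apply to up to 30 enrolled patients. The protocol gives no event rates, so the number of affected events cannot be stated. The risk is late or misrouted notice, and no endpoint, analysis or sample-size figure is touched.

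**What to change.** Amend the closing paragraph of Adverse Event Documentation:

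1. Replace the company name with the trial party that holds the regulatory filing duty.
2. State which party is meant by the study sponsor in the 24-hour rule.
3. Make the trigger *any serious or severe adverse event or device-related unanticipated event*. Keeping *severe* beside *serious* means that no event now covered drops out.

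As clean-up only, reconcile the two definitions of a UADE: the one under Unanticipated Adverse Events starts from any adverse effect, and the one under its own heading starts from a serious adverse event. Also check whether the two items on implant loosening and on dislocation from implant positioning belong in the study-device list. The documents do not settle which text to keep in either case.

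The cost is a text amendment and possibly a few more expedited reports.

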Skin and Subcutaneous Tissue Reaction/Allergy	
• Desiccation/injury• Skin rash, irritation, blistering• Pruritus/itching• Skin excoriation/breakdown• Skin stripping• Skin scarring if significant skin irritation were to occur• Maceration• Skin hyper/hypo-pigmentation at and/or around dressing application area• Erythema/redness, edema, inflammation, or swelling at and/or around dressing application area
Mild Pain or Discomfort	
• Tenderness/minor ache at and/or around dressing application area• Perspiration associated with wearing dressing• Auditory irritation (due to mild buzzing sound of negative pressure unit)• Decreased sleep or sleep quality• Paresthesia (numbness, tingling, prickling, creeping sensation)

Other	
 • Bleeding • Cardiac compromise (vagal response, bradycardia) • Pulmonary compromise • Accidental instillation in a body cavity • Localized infection • Autonomic dysreflexia (in subjects with spinal cord injury) • Retained foreign debris (e.g.foam) in the wound • Impairment of mobility/activity (limitation secondary to weight and attachment of therapy unit) • Possible tubing entanglement/trip or slip hazard leading to fracture, tissue damage • Incorrect therapy unit settings resulting in incorrect frequency/dosing • Tunneling • Stalled healing/non-progression of healing • Deterioration of the wound • Systemic reaction (due to allergic reaction to dressing materials) • Burn secondary to therapy unit or power cord malfunction
-------	---

Prontosan:

In very rare cases there may be a mild burning sensation after Prontosan is applied. This should subside after a few minutes. In Rare cases (less than 1 out of 10,000), anaphylactic shock has been reported after the use of Prontosan. Protosan can also cause allergic reactions such as itching and rashes.

Quality Assurance of Data Collection:

Patient confidentiality is maintained by adherence to the rules of HIPAA and the University of Missouri IRB. Close assessment of perioperative events and complications will be performed to ensure no significant deleterious effects are resulting from research activity.

Statistical analysis plan:

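### The two Expectedness definitions are not complementary: an SAE listed in kind but beyond its documented severity or incidence meets Expected and, on one reading, Unexpected as well

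*Protocol*

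**What the plan says.** All SAEs are to be classified under the protocol's Expectedness section by two definitions.

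- The first gives the condition for calling an SAE foreseen: "Expected, Anticipated: the effect, problem, or death had been previously identified in nature, severity, or degree of incidence in the study or product documentation".
- The second gives the opposite label, and repeats the three attributes under a negation: "Unexpected, Unanticipated: if that effect, problem, or death was not previously identified in nature, severity, or degree of incidence". It points to the same documentation as the first.

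Three neighbouring definitions cover related ground:

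- Under Unanticipated Adverse Events, a UAE is "any adverse reaction, the nature and severity of which is not consistent with the applicable product information". Incidence is not mentioned.
- Under the same heading, a first UADE definition says that "the effect must not have been previously identified in the Investigational Plan or Instructions for Use in its nature, frequency or severity".
- Under Unanticipated Adverse Device Effect (UADEs), a second one applies to an effect that "was not previously identified in nature, severity, or degree of incidence in the investigational plan or application". It cites 21 CFR 812.3.

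The Prontosan risk text gives the only numeric rate in the safety sections: "In Rare cases (less than 1 out of 10,000), anaphylactic shock has been reported after the use of Prontosan".

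On reporting, the section UADE Reporting to KCI, USA Inc. sends both UADEs and SAEs to KCI and the IRB. The end of Adverse Event Documentation requires 24-hour notice to the sponsor for two kinds of event: any severe adverse event, and any device-related unanticipated event.

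**The concern.** Two classes meant to divide all SAEs should be complements, so that each event falls in exactly one. Here one phrase is used first affirmatively and then under a negation, with the 'or' unchanged. The affirmative form is satisfied by a single match. An event that is known in kind, but more severe or more frequent than documented, is therefore expected on the wording. Whether it is also unexpected depends on how the negated 'or' is read, and nothing in the protocol says which definition prevails.

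Two assessors could thus label the same SAE differently, and both would be following the text. In a pilot with about 10 instilled subjects, a known type of event at an unusual rate or severity is one form that a safety signal could take, and this is the case that the wording leaves unsettled.

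**Working it through.** The protocol gives no figure of its own to reproduce on this point. The check has three parts.

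**1. The definitions as logic.** Let N, S and I stand for nature, severity and degree of incidence having been previously identified. Each is true or false, so there are 2 × 2 × 2 = 8 combinations.

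- Expected as written is N or S or I. It is false only when all three are false, so 7 of 8 combinations are expected.
- Unexpected, reading A (none identified), is true in 1 of 8. The overlap with Expected is 0, and a match on nature alone settles the label as expected.
- Unexpected, reading B (any one not identified), is true in 7 of 8. Only the combination with all three true is excluded. The overlap with Expected is 7 + 7 − 8 = 6 of 8.

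An event listed in kind has N true, so it meets Expected under either reading. Under reading B it also meets Unexpected as soon as S or I fails. These are counts of logical cases, not probabilities of events.

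**2. An example from the protocol's own figures.** Inputs: documented rate below 0.0001 (Prontosan risk text); 10 patients per group (Study Design); up to 30 enrolled (Study Design), which is 15 per arm if split equally (assumption). The rate is taken as per patient (assumption).

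- Expected count at the bound, n = 10: 10 × 0.0001 = 0.001.
- P(at least one case), n = 10: 1 − (1 − 0.0001)^10 = 0.0010, or 0.10%.
- P(at least one case), n = 15: 1 − (1 − 0.0001)^15 = 0.0015, or 0.15%.
- One case in 10 is an observed 10%, and 0.10 / 0.0001 = 1,000. Because the documented rate is an upper bound, the ratio is at least 1,000.
- Exact 95% interval for 1 of 10: 0.25% to 44.5%. The lower limit is about 25 times the bound (0.0025 / 0.0001).
- Exact 95% interval for 1 of 15: 0.17% to 31.9%.

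In the notation above, this event has N and S true, and I fails because the observed frequency exceeds the documented one. It meets Expected as written. Under reading B it also meets Unexpected.

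The per-patient assumption matters. If the rate were per instillation, one dressing period of 72 to 96 hours on a 2-hour cycle gives about 72/2 = 36 to 96/2 = 48 instillations per subject, or 360 to 480 in 10 subjects. Then P(at least one case) at the bound is 1 − 0.9999^360 = 3.5% to 1 − 0.9999^480 = 4.7%. The protocol does not state the unit.

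**3. What the label can change.** Every SAE goes to KCI and the IRB whatever its label, and every severe AE goes to the sponsor within 24 hours. The first 24-hour trigger is severity, not seriousness. An SAE can qualify through an intervention to prevent permanent impairment (Serious Adverse Events). It could still be graded moderate if it needs treatment but no extended hospitalization or intensive care (Adverse Event Documentation). If such an event is device-related, only the second trigger, being unanticipated, can bring it under the 24-hour rule.

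**The case against.** The best case on the other side is that this is loose drafting with little consequence. Several parts of it stand.

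- A reader might infer that expectedness decides whether an SAE is a UADE. The protocol does not say so. UADE is defined separately, in two places, with its own reference documents and a catch-all for other serious problems, and neither definition refers to the Expectedness bullets.
- A reader might infer that a signal would go unreported. The reporting rules do not support that. Anaphylactic shock would plausibly be graded severe and be serious, so it would reach the sponsor within 24 hours, and KCI and the IRB as an SAE.
- A reader might infer a one-way rule under which such an event is expected and nothing else. That follows only under reading A. Under reading B it is in both classes.
- The example shows excess incidence only, since anaphylactic shock is already listed at that severity. With 10 subjects any single event is 10%, so the large ratio owes much to the size of the arm.
- The UAE definition concerns adverse reactions judged against product information. It is a neighbouring category to be aligned, not a competing rule for SAE expectedness.
- The anticipated-event lists are broad and include deep and superficial infection, cardiac arrest and delayed wound healing. The protocol nevertheless offers no basis for saying that they cover nearly every serious event.
- A fix that always demanded a match on frequency would not work, because apart from anaphylactic shock the safety text gives no rates.

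None of this makes the two definitions complementary, and no other passage settles which one governs.

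**Conclusion.** The point holds as a defect in a stated rule, not as missing detail. As written, an SAE known in kind always meets Expected, even when it exceeds its documented severity or incidence. On the reading that the UADE definition appears to intend, 6 of 8 attribute combinations are both expected and unexpected. The anaphylaxis example gives the scale: a chance of about 0.1% or less in 10 subjects (0.15% in 15) if the documented rate is per patient, and an observed rate at least 1,000 times the documented bound, for an event that could still be filed as expected.

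The consequence is limited. No endpoint, analysis or sample size is affected, and most reporting runs regardless of the label. What depends on the wording is the consistency of the expected/unexpected label, and whether the 24-hour rule applies to device-related unanticipated events not graded severe. The correction is worth making because it is specific, cheap and bears on safety.

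**What to change.** Replace the two bullets under Expectedness with one rule and its complement. An SAE is expected only if it is consistent with the reference documents in nature, in severity and, where a rate is documented, in incidence. It is unexpected if any one of these is not met. Where no rate is documented, judge on nature and severity alone.

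In the same edit:

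- Name one set of reference documents. The present definitions point variously to product information, the investigational plan, the instructions for use, an application, and study documentation.
- Reconcile the bullets with the UAE definition, which joins nature and severity by 'and' and omits incidence, and with the two UADE definitions.
- State whether the documented anaphylaxis rate is per patient or per use, so that the incidence criterion can be applied.

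The cost is a short protocol change, with more SAEs classed as unexpected. Where a rate is documented, the combinations that count as expected fall from 7 of 8 to 1 of 8. Where none is documented, they fall from 3 of 4 (nature or severity) to 1 of 4 (nature and severity). How many actual events would move cannot be worked out from the protocol.
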